14.3.5 Testing strategy

There will be no formal testing. All confidence intervals (CIs) will be presented with two-sided 95% degree of confidence.

14.3.6 Analysis of primary efficacy endpoints

Two estimands addressing different aspects of the trial objectives will be defined:

- Primary estimand: ‘composite’.
- Secondary estimand: ‘treatment policy’.

The applied estimands incorporate 2 main types of events that influence how the treatment effects are estimated (i.e. initiation of rescue treatment and permanent discontinuation of IMP).

- **Initiation of rescue medication:** Some of the estimands use the initiation of rescue medication as an event that modifies the applied value of an endpoint, e.g. by defining a subject receiving rescue medication as a non-responder.
- **Permanent discontinuation of IMP:** This event occurs when a subject is permanently withdrawn from the treatment or the trial as described in Section 10. This can either happen at his/her own initiative or at the investigator’s discretion. The event also includes the possibility of a subject being lost to follow-up. The timing of the event is defined as the date of the early termination visit for withdrawn subjects or – in the case of a subject lost to follow-up – the date of the last known visit to the clinic. As for the rescue medication, the event type is used to modify an applied endpoint value.

All efficacy analyses will be based on the full analysis set.

14.3.6.1 Primary estimand: ‘composite’

The primary estimand for the primary endpoints will be:

- Treatment difference in response rates of IGA 0/1 and EASI75 after 16 weeks achieved without rescue medication, regardless of treatment discontinuation.

The primary estimand assesses the expected difference in response rates (defined as response obtained without initiation of any rescue medication) after 16 weeks, resulting from initiation

of a treatment regimen with tralokinumab+TCS compared to a treatment regimen with placebo+TCS.

Primary analysis for the primary estimand

Data retrieved at Week 16 for subjects who have permanently discontinued IMP prior to Week 16 will be included in the analysis. Subjects who prior to the Week 16 visit have received rescue medication will be considered non-responders, reflecting an assumption that initiation of rescue medication indicates failure of the randomised treatment to achieve response, and that a (possible) observed positive response after initiation of rescue medication is not attributable to the randomised treatment. Missing data for subjects who do not attend the Week 16 visit and where rescue medication has not been used prior to Week 16, will be imputed as non-responders.

The difference in response rates between treatment groups will be calculated by the Mantel-Haenszel method stratified by baseline disease severity (IGA 3 or 4). The treatment difference and the corresponding 95% CI will be presented.

Sensitivity analysis

The purpose of the analysis is to assess the robustness of results of the primary analysis with respect to the retrieved data at Week 16.

All subjects who have permanently discontinued IMP prior to Week 16 will be imputed as non-responders, even if no rescue medication has been used. This is to reflect a situation where retrieved efficacy data and concomitant medications could be registered less accurately for subjects who have discontinued treatment. The same Mantel-Haenszel method as used for the primary analysis will be applied including stratification by baseline disease severity.

14.3.6.2 Secondary estimand: ‘treatment policy’

The secondary estimand for the primary endpoints will be:

- Treatment difference in response rates of IGA 0/1 and EASI75 after 16 weeks regardless of rescue medication and discontinuation of IMP.

The secondary estimand assesses the average difference in response rates, resulting from initiation of a treatment regimen with tralokinumab+TCS and additional rescue medication as compared to a treatment regimen with placebo+TCS and additional rescue medication.

Primary analysis for the secondary estimand

All data used as observed at Week 16 regardless of rescue medication and discontinuation of IMP, thus data retrieved at Week 16 for subjects who have permanently discontinued treatment prior to Week 16 will be included in the analysis.

IGA 0/1 responder imputation

Imputation of missing binary IGA 0/1 data at Week 16 will be done using multiple imputations of the underlying 5-point IGA values within the 4 groups defined according to randomised treatment arm and whether or not subjects have permanently discontinued IMP prior to Week 16 assuming that data is missing at random within each arm. Within a given treatment arm, retrieved data from discontinued subjects will be used to impute missing data for other discontinued subjects. Similarly, the available data from not discontinued subjects will be used to impute data for such subjects where the Week 16 value is missing.

1. In each group, intermittent missing values will be imputed using last observation carried forward (LOCF) to obtain a monotone missing data pattern.
2. An ordinal logistic regression model assuming proportional odds will be fitted to the IGA value at Week 2. The model will include effect of baseline disease severity (IGA 3 or 4) as factor. The estimated parameters, and their variances, will be used to impute missing IGA values at Week 2. 100 copies of the dataset will be generated (seed=16201343).
3. For each of the 100 copies of the dataset, missing values at Week 4 will be imputed in the same way as for Week 2. The imputations will be based on a proportional odds logistic regression model with effects of baseline disease severity (IGA 3 or 4) together with the IGA value at Week 2 as factors. The estimated parameters, and their variances, will be used to impute missing values at Week 4.
4. This stepwise procedure will then be repeated sequentially for Weeks 6, 8, 10, 12, 14, and 16 with the modification that only the IGA values from the 2 preceding visits will be included as factors in addition to baseline disease severity. The missing binary IGA 0/1 response at Week 16 will be derived from the corresponding underlying imputed IGA value.

For not discontinued subjects, the stepwise multiple imputations procedure will be conducted as described above.

For discontinued subjects, it is expected that the number of subjects with retrieved data at Week 16 will be too small to facilitate the same imputation model as mentioned above. Consequently, an imputation model with only baseline effects (IGA as a factor) will be

applied for discontinued subjects. Some factors may have to be omitted, depending on the observed data, e.g. if retrieved subjects all have the same baseline severity.

EASI75 responder imputation

Imputation of missing binary EASI75 data at Week 16 will be done using multiple imputations of the underlying 72-point EASI values within the 4 groups defined according to randomised treatment arm and whether or not subjects have permanently discontinued IMP prior to Week 16 assuming that data is missing at random within each arm. Within a given treatment arm, retrieved data from discontinued subjects will be used to impute missing data for other discontinued subjects. Similarly, the available data from not discontinued subjects will be used to impute data for such subjects where the Week 16 value is missing.

1. Intermittent missing values will be imputed in each group using a Markov Chain Monte Carlo method to obtain a monotone missing data pattern and 100 copies of the dataset will be generated (seed=11101343).
2. For each of the 100 copies of the dataset, an ANCOVA model will be fitted to the EASI value at Week 2. The model will include effects of baseline EASI as a covariate, and baseline disease severity (IGA 3 or 4) as factor. The estimated parameters, and their variances, will be used to impute missing EASI values at Week 2 (seed=16201343).
3. For each of the 100 copies of the dataset, missing EASI values at Week 4 will be imputed in the same way as for Week 2. The imputations will be based on the same ANCOVA model with effects of baseline EASI as a covariate, and baseline disease severity (IGA 3 or 4) as factor together with the EASI value at Week 2 as covariate. The estimated parameters, and their variances, will be used to impute missing values at Week 4.
4. This stepwise procedure will then be repeated sequentially for Weeks 6, 8, 10, 12, 14, and 16 with the modification that only the EASI values from the preceding 2 visits will be included as covariates in addition to baseline EASI as a covariate, and baseline disease severity as factor. The missing binary EASI75 response at Week 16 will be derived from the corresponding underlying imputed EASI value.

For not discontinued subjects, the stepwise multiple imputations procedure will be conducted as described above.

For discontinued subjects, it is expected that the number of subjects with retrieved data at Week 16 will be too small to facilitate the same imputation model as mentioned above. Consequently, an imputation model with only baseline effects (IGA as a factor and EASI as a

covariate) will be applied for discontinued subjects. Some factors may have to be omitted, depending on the observed data, e.g. if retrieved subjects all have the same baseline severity.

Analysis of Week 16 response

For each of the imputed data sets, the difference in response rates (either the IGA 0/1 or the EASI75) between treatment groups will be calculated using the same Mantel-Haenszel method as used for the primary analysis of the primary estimand including stratification by baseline disease severity (IGA 3 or 4). The estimates and standard errors from the 100 analyses will be pooled to one estimated treatment difference and associated standard error using Rubin's rule to draw inference. From these pooled estimates, the 95% CI for the treatment difference will be calculated.

Sensitivity analysis for secondary estimand

The primary analysis of the secondary estimand assumes that discontinued subjects with missing data at Week 16 behave similarly to discontinued subjects with available (retrieved) Week 16 data.

The robustness of this assumption is evaluated in a sensitivity analysis, applying single imputation to deem all subjects with missing data at Week 16 as 'non-responders'. The same Mantel-Haenszel method as used for the primary analysis of the primary estimand will be applied including stratification by baseline disease severity.

14.3.7 Analysis of key secondary efficacy endpoints

The binary key secondary endpoint, reduction of Worst Daily Pruritus NRS (weekly average) ≥ 4 from baseline to Week 16, will be analysed as described for the primary endpoint EASI75 using both estimands with the modification of the ANCOVA imputation model that reduction of Worst Daily Pruritus NRS weekly average replaces EASI where preceding values are used as covariates.

For the continuous key secondary endpoints, change from baseline to Week 16 in SCORAD and DLQI, 2 estimands addressing different aspects of the trial objectives will be defined:

- Primary estimand: 'composite'.
- Secondary estimand: 'hypothetical'.

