8.2 Inclusion criteria

The subjects must fulfil all of the following criteria to be eligible for the trial:

1. Signed and dated informed consent has been obtained prior to any protocol-related procedures. The subject's legally authorised representative must sign the informed consent if the subject is below 20 years of age.
2. Japanese subject aged 18 years and above.
3. Diagnosis of AD as defined by the Hanifin and Rajka (1980) criteria for AD ([21](#)) ([Appendix 4](#)).
4. History of AD for ≥ 1 year.
5. Subjects who have a recent history (within 1 year before screening) of inadequate response to treatment with topical medication.
 - Inadequate response is defined as failure to achieve and maintain remission or a low disease activity state (comparable to IGA 0 [clear] to IGA 2 [mild]) despite treatment with a daily regimen of TCS of medium or higher potency (\pm TCI as appropriate) applied for at least 28 days or for the maximum duration recommended by the product prescribing information (e.g. 14 days for strongest TCS), whichever is shorter.
 - Subjects with documented systemic treatment for AD in the past year are considered as inadequate responders to topical treatment and are potentially eligible for treatment with tralokinumab after appropriate washout.

6. AD involvement of $\geq 10\%$ body surface area (BSA) at screening and baseline according to component A of SCORAD.
7. An EASI score of ≥ 12 at screening and ≥ 16 at baseline.
8. An IGA score of ≥ 3 at screening and at baseline.
9. A Worst Daily Pruritus NRS average score of ≥ 4 during the week prior to baseline.
 - Worst Daily Pruritus NRS score at baseline will be calculated from daily assessments of worst itch severity (Worst Daily Pruritus NRS) during the 7 days immediately preceding randomisation (Day -6 to Day 0). Worst Daily Pruritus NRS scores must be reported for a minimum of 4 out of the 7 days to calculate the baseline average score. For subjects who do not fulfil this requirement, randomisation should be postponed until this requirement is met, but without exceeding the 6 weeks' maximum duration for screening.
10. Subjects must have applied a stable dose of emollient twice daily (or more, as needed) for at least 14 days before randomisation.
11. Women of childbearing potential must use a highly effective* form of birth control throughout the trial and for at least 16 weeks (5 half-lives) after last administration of IMP.

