6.6.1 Primary efficacy endpoints

Primary analysis for the secondary estimand

As described in the protocol, imputation of missing data at Week 16 will be done using multiple imputations within 4 groups defined according to treatment group and whether or not subjects have permanently discontinued IMP prior to Week 16 assuming data is missing at random (MAR). Imputation within one or more groups may not be feasible if too few data is available. If this is the case, the primary analysis will not be conducted and will be replaced by the corresponding sensitivity analysis where subjects with missing data will be imputed as non-responders.

6.6.2 Key secondary efficacy endpoints:

Reduction of Worst Daily Pruritus NRS (weekly average) of at least 4 from baseline to Week 16 will be based on subjects in the FAS with a baseline Pruritus NRS weekly average of at least 4.

The binary endpoint is planned to be analysed as described for the primary endpoint EASI75 using the two estimands. It is however expected that subjects will not fill in the eDiary when they have discontinued treatment, and it is considered likely, there will be no nominal Week 16 data available for discontinued subjects. If this is the case, the primary analysis of the secondary estimand ('treatment policy') will not be performed for this endpoint. The corresponding sensitivity analysis for the secondary estimand, analysing subjects with missing Week 16 data as non-responders, while otherwise using observed data for the remaining subjects, will still be conducted.

SCORAD

Trial ID: LP0162-1343	Date: 15-Jun-2021	Version: 1.0 Page 11 of 22
-----------------------	-------------------	-------------------------------

For the calculation of SCORAD, the protocol states that dryness is evaluated on uninvolved areas. This means that if a subject has an extent, i.e. total body surface area (BSA) affected by AD, of 100% then there is no area to score. In the event that dryness is missing and extent is 100% then a dryness score of 0 (none/absent) will be imputed.

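### As written, the treatment-policy imputation of the pruritus responder endpoint keeps baseline EASI and leaves out baseline itch

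*Protocol*

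**What the plan says.** Protocol 14.3.6.2 sets out the EASI75 imputation that serves as the template. At the first step, "The model will include effects of baseline EASI as a covariate, and baseline disease severity (IGA 3 or 4) as factor". At the later steps, "only the EASI values from the preceding 2 visits will be included as covariates in addition to baseline EASI as a covariate". For subjects who have discontinued IMP it prescribes "an imputation model with only baseline effects (IGA as a factor and EASI as a" covariate).

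Protocol 14.3.7 applies this to the pruritus responder endpoint with a single modification: "reduction of Worst Daily Pruritus NRS weekly average replaces EASI where preceding values are used as covariates". Nothing is said about replacing baseline EASI, and the variable to be imputed is not named.

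SAP 6.6.2 refers back to the EASI75 analysis and restricts the endpoint to "subjects in the FAS with a baseline Pruritus NRS weekly average of at least 4". It considers it likely that discontinued subjects will have no diary data at nominal Week 16. In that case the multiple-imputation analysis is not done and only the version counting missing as non-response remains. SAP 6.6.3 truncates Week 16 draws to the limits of the parameter's scale.

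The composite (primary) estimand in Protocol 14.3.6.1 has no imputation model: missing Week 16 data where "rescue medication has not been used prior to Week 16, will be imputed as non-responders". Response rates are compared by the "Mantel-Haenszel method stratified by baseline disease severity (IGA 3 or 4").

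Baseline itch is already collected. Protocol 8.2 averages daily scores "during the 7 days immediately preceding randomisation (Day -6 to Day 0") and requires at least 4 of the 7 days before randomisation.

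**The concern.** Whether a subject can fall by 4 points depends on where that subject started. The scale runs from 0 to 10, so someone starting at 4.2 must reach 0.2 or below. A model for the reduction without the starting score gives low-baseline subjects much the same imputed chance of response as high-baseline subjects, and can draw reductions that the scale does not allow.

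It is also out of line with the rest of the plan. EASI75 is imputed from baseline EASI. SCORAD and DLQI are imputed from their own baselines in the copy-reference analysis (Protocol 14.3.7.2) and analysed with the baseline value in the model (14.3.7.1). The continuous pruritus endpoint uses the repeated measurements model with baseline by visit (14.3.8). Only the pruritus responder imputation lacks its own baseline.

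At stake are the treatment-policy estimate for a key secondary endpoint, if missingness is related to baseline itch, and reproducibility, because two programmers could code the present text differently.

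**Working it through.** The documents give no figure on this point to reproduce: no expected response rate, SD, correlation or missingness. The structure follows from the text; the sizes rest on assumptions.

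**Structure.** Write B for baseline NRS, Y for the Week 16 weekly average and R = B − Y for the reduction. In a sequential scheme the preceding values are the quantities imputed at earlier steps, so the natural reading is that R is imputed:

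- not discontinued: R ~ baseline EASI + IGA + two preceding R values;
- discontinued: R ~ baseline EASI + IGA.

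Counting baseline among the preceding values does not help, since the reduction at baseline is B − B = 0 for everyone. Because Y cannot be below 0, R cannot exceed B, yet the model has no such limit. Capping R at B would not repair responder status: every analysed B is at least 4, so a draw above B still counts as a response after capping.

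**Assumptions.** B normal (7.5, 1.4) truncated to 4–10; residual SD 2.2; correlation of baseline EASI with itch 0.3; response about 26% versus 44%; slope b of Week 16 itch on baseline itch from 0.3 to 0.9. The comparison model imputes Y from B and IGA (plus two preceding Y values if not discontinued), truncates to 0–10 and derives R.

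**Imputed response by baseline band**

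| | b=0.3 | 0.5 | 0.7 | 0.9 |
|---|---|---|---|---|
| Baseline 4–5: true | 0.105 | 0.160 | 0.224 | 0.311 |
| Plan, discontinued | 0.327 | 0.326 | 0.330 | 0.337 |
| With baseline NRS, discontinued | 0.097 | 0.138 | 0.203 | 0.272 |
| Plan, not discontinued | 0.117 | 0.152 | 0.210 | 0.276 |
| With baseline NRS, not discontinued | 0.091 | 0.137 | 0.187 | 0.260 |
| Baseline 9–10: true | 0.585 | 0.517 | 0.451 | 0.388 |
| Plan, discontinued | 0.363 | 0.359 | 0.351 | 0.344 |

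In the 4–5 band under the plan's model, 23–24% of draws for discontinued subjects exceed the subject's own baseline, and these make up 72–74% of that group's imputed responders. For subjects who have not discontinued, the figures are 7–18% of draws and 58–64% of imputed responders. With the comparison model none exceed baseline.

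The plan's model overstates response at low baseline and understates it at high baseline, so the errors largely cancel. At b=0.3 the overall imputed rate for discontinued subjects is 0.347 with the plan's model and 0.348 with baseline NRS. The 4–5 band holds 3.2% of simulated subjects; with 10% missing, that is 100 × 0.032 × 0.10 = 0.32 subjects.

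**Error in the treatment difference** (imputed minus true; 10% missing, half of them discontinued)

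| Missingness | b=0.3 | 0.5 | 0.7 |
|---|---|---|---|
| Random | 0.1677−0.1674 = +0.0003 | 0.1770−0.1762 = +0.0008 | 0.1781−0.1782 = −0.0001 |
| Commoner at low baseline, both arms | 0.1700−0.1690 = +0.0010 | 0.1734−0.1730 = +0.0004 | 0.1792−0.1788 = +0.0004 |
| Low baseline in tralokinumab, high in placebo | 0.1782−0.1724 = +0.0058 | 0.1821−0.1768 = +0.0053 | 0.1804−0.1776 = +0.0028 |

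The comparison model's own errors in these runs lie between −0.0016 and +0.0001, so differences near 0.001 should not be read as real. The half-width of the 95% CI at 50 per arm is 1.96 × 0.0953 = 0.187 at b=0.3.

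**Adjusting the comparison for baseline itch.** Over 4,000 simulated trials of 100 subjects, the variance of an IGA- and itch-adjusted risk difference relative to Mantel-Haenszel was 0.938, 0.972, 0.997 and 1.012 for b = 0.3, 0.5, 0.7 and 0.9.

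**The case against.** The strongest reply is that this hardly matters. The composite analysis does not use the model. The SAP expects that the analysis which does use it may not be run. Even if it is run, the non-responder sensitivity analysis accompanies it. For subjects who have not discontinued, the preceding reductions carry most of the missing baseline information. The low-baseline band is a small share of subjects. All of this stands. The SAP's fallback is conditional, however: if some discontinued subjects return Week 16 diary data, the model can run. It would then also fill in subjects still on IMP who have fewer than 4 of 7 diary days.

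A second reply is that the text is a short template substitution, so the omission may be a drafting gap rather than a choice. That is fair, and the documents do not settle it. If a programmer imputed Y instead of R, truncation at 0 would remove reductions above baseline, but baseline itch would still be missing from the model. The gap therefore needs closing on either reading.

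Third, a normal model for Y also produces draws outside the scale, so their frequency does not measure bias. Correct; the case rests on the imputed response rates by baseline band.

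**Conclusion.** The point holds for the imputation model under the treatment-policy estimand and no further. As written, the model omits baseline NRS, and for discontinued subjects it contains no itch variable. Under the assumed inputs, discontinued subjects with baseline 4 to 5 receive about 33% imputed response against 11% to 31% true. The excess is largest when Week 16 itch depends weakly on baseline itch and nearly vanishes at slope 0.9. The effect on the treatment difference is small: at most about 0.001 when missingness is random or depends on baseline alike in both arms, and 0.003 to 0.006 when it runs in opposite directions by arm.

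These sizes depend on assumed distributions and missingness. In the treatment-difference check, the models were also fitted to all subjects in the arm with observed Week 16 data, not only to retrieved discontinued subjects.

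A reader might infer four stronger things that the documents do not support:

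- *The endpoint's main result is affected.* It is not; the composite analysis uses non-responder imputation.
- *Low-baseline subjects cannot respond.* Every analysed baseline is at least 4, so a reduction of 4 is attainable; only reductions above baseline are impossible.
- *Stratifying by IGA alone is an error or wastes assured precision.* It matches the randomisation and is valid. The variance gain from adjustment is about 0–6% and may be nil, and no formal testing is planned.
- *The Week 15 average is ignored.* The week grid for this endpoint is not stated, so this cannot be established.

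This is a nearly costless improvement and clarification, not a threat to the trial's conclusions.

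**What to change.** In Protocol 14.3.7 or SAP 6.6.2, state that for the treatment-policy analysis:

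- the imputed variable is the weekly-average Worst Daily Pruritus NRS, not its reduction;
- baseline NRS replaces baseline EASI, alongside baseline IGA;
- for subjects who have not discontinued IMP, the preceding weekly averages are added, on a named week grid (even weeks or every week);
- for discontinued subjects the model uses baseline NRS and baseline IGA;
- Week 16 values are truncated to 0–10, and the reduction and responder status are then derived.

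Keep the SAP's fallback and the IGA-stratified Mantel-Haenszel analysis. A supportive risk difference adjusted for baseline NRS and IGA is optional.

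The cost is a few sentences and a few lines of code, with no new data. The one drawback is that the model no longer mirrors the EASI75 template; keeping Mantel-Haenszel preserves comparison with LP0162-1339. The change should be made before the randomisation code is broken.
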